**STATISTICAL ANALYSIS PLAN
FOR CLINICAL TRIAL**

Principal Investigator: [name]

[name], PT

Eastern Mediterranean University

Health Sciences Faculty

Physiotherapy and Rehabilitation Department

[name]

Official Study Title: The Comparison of Virtual and Real Boxing Training in Hemiparetic Stroke Patients: a Randomized Controlled Study

Clinical trial number: NCT03651479

Protocol ID: 2018/02(a)-08

Date: 09/08/2019

[figure not shown]
Table of contents

1. Introduction
2. Study design
3. Sample size calculation
4. Aims and objectives
5. Outcomes
 - a. Primary outcome
 - b. Secondary outcomes
6. Statistical Methodology
7. References

Contents

- 1. Introduction:** The most common presentation of a stroke patient requiring rehabilitation is contralateral hemiparesis or hemiplegia. Upper extremity hemiparesis is one of the most common conditions requiring rehabilitation and upper extremity dysfunction occurs in rates ranging from 30% to 66%.¹ Upper extremity functional recovery is often slower than the recovery of lower extremity functions.^{1,2} Only a small portion of stroke patients with upper limb motor impairment (12%) is able to regain full function, while the majority of the patients require constant care from family or social services.³ The aim of this study is to compare the effects of virtual and real boxing training on upper extremity functions (primary outcome measure), cognitive functions, balance functions and activities of daily living (secondary outcome measures) in hemiparetic individuals with stroke. This statistical analysis plan (SAP) will give more detailed descriptions of the endpoints in the study and the corresponding analyses.
- 2. Study design:** In this study participants who had a documented diagnosis of stroke from their neurologist from the local community will be screened for eligibility. The participants who are being diagnosed as first time ever stroke, who has hemiparesis, who are between the ages of 18-70, who has Mini Mental Test score ≥ 23 , whose functional level is less than 4 according to the Modified Rankin Scale and who has upper extremity spasticity < 3 on Modified Ashworth Scale will be included in this study. Individuals will be excluded from the study if they have any of the following criteria: hypertension, heart disease, subluxation and fracture at the shoulder, visual impairment, limitation in passive normal joint movement in hemiplegic side and botulinum toxin administration or surgical operation in the last 6 months. If the participants are eligible to participate they will be randomized to either the virtual boxing group (VBG) or the real boxing group (RBG). Each participant will be randomly assigned to either treatment group with simple randomization (odd - even numbers: odd numbers will represent VBG and even number will represent RBG). The study protocol is presented in *Study protocol - CONSORT diagram* below.
- 3. Sample size calculation:** Sample size will be calculated by using G* Power 3.1.9.2 program. The mean and standard deviation values are taken as a reference from the study of Jo et al.⁴ Statistical power analysis calculations suggested 15 subjects for each group ($\alpha = 0.05$, 95% confidence interval), considering the dropouts the number was increased by 33% and finally 20 subjects planned to be included for each group. Based on the power calculation ($n=20+20$) we will enroll 40 individuals in each treatment group; $n=20$ in virtual boxing group (VBG) and $n=20$ in real boxing group (RBG).

Study protocol (CONSORT diagram)

4. Aims and objectives: To compare the effects of virtual and real boxing training on upper extremity functions (primary outcome measure), cognitive functions, balance functions and activities of daily living (secondary outcome measures) in hemiparetic individuals with stroke.

5. Outcomes: This section will present the outcomes investigated to answer the study aims and objectives.

5.1. Primary outcome: The primary outcome is Wolf Motor Function Test (WMFT) which quantifies upper extremity motor ability through the use of timed and functional tasks. The original version of the WMFT was developed by Wolf et al in 1989 to examine the patients with moderate to severe upper extremity motor deficits.⁵ Then, the modified version of the test was developed by Taub et al to assess the motor abilities of chronic patients who had suffered mild to moderate stroke.⁶ The widely used version of the WMFT consists of 17 items, items 7 and 14 are related to subject strength and the other 15 to subject functional ability during various tasks. Performances are scored using a 6-point functional ability scale and the less affected upper extremity followed by the most affected side. The total score, also referred to as Functional Ability score (WMFT-FAS), is the sum of the 15 items score (with a 6-point ordinal score from 0 to 5). The maximum

total score is 75, with lower scores indicating lower functional levels.⁷ It will be measured at baseline (0 weeks) and at the completion of the treatment (8 weeks). The change in scores from Baseline to 8 weeks will be calculated.

5.2. Secondary outcomes: Minnesota Manual Dexterity Test (MMDT), Video Boxing Analysis (VBA), Fullerton Advanced Balance (FAB), Addenbrook Cognitive Assessment (ACE-R) and Frenchay Activity Index (FAI). The secondary outcome will be measured at the baseline (0 weeks) and at the completion of the treatment (8 weeks). The change in scores from Baseline to 8 weeks will be calculated. The estimated difference in mean change from baseline to 8 weeks and the corresponding 95 % confidence interval (CI) will be presented.

5.2.1. Minnesota Manual Dexterity Test (MMDT): MMDT measures the speed of gross arm and hand movements (arm-hand dexterity) during rapid eye-hand coordination tasks. The MMDT material consists of a plastic collapsible board with 60 holes and 60 cylindrical blocks (3.7 cm in diameter and 1.9 cm high). The MMDT involve five subtests: Placing Test, Turning Test, Displacing Test, One-hand Turning and Placing Test, and the Two-hand Turning and Placing Test. The Placing Test (1st item: taking the blocks with one hand and putting them in the holes on the board in a standardized order) and Two-hand Turning and Placing Test (5th item: taking the blocks with two hands and putting them in the holes on the board in a standardized order) were the two items selected for this study. Participants were given a 15 second trial for both items. The test was timed with a stopwatch and each item was measured three times. The number of seconds it took to complete the task on each of the trials was recorded. An average score from the three trials was calculated. The high performer should score higher on the MMDT than the low performers.^{8,9}

5.2.2. Video Boxing Analysis (VBA): For boxing analysis patients were videotaped while punching with their right side, punching with side left and punching bilaterally. Than the videotape were watched to analyze and the number of right unilateral punches in 1 minute, number of left unilateral punches in 1 minute and number of bilateral punches in 1 minute were recorded. This analysis were done for the quantitative assessment of punch number per minute (number of punch/minute). This measurement method is created and constructed by the authors of this study. The lower the score, the better the outcome.

5.2.3. Fullerton Advanced Balance (FAB): The FAB scale is a performance-based scale which was developed to evaluate changes in many aspects of balance.¹⁰ The FAB scale consists of 10 test items for the evaluation of static and dynamic balance status. These test items are: 1. Feet together, eyes closed, 2. Reach forward to retrieve an object, 3. Turn in a full circle, 4. Step up and over a bench, 5. Tandem walk, 6. Stand on one leg, 7. Stand on foam, eyes closed, 8. Two-footed jump, 9. Walk with head turns, 10. Reactive postural control. Each test

item is scored using a 0-4 scale. The highest score indicating better balance abilities is “40” points, and the lowest is “0”. The FAB-T (Fullerton Advanced Balance – Turkish) scale was found to be a reliable and valid measurement of balance in Turkish population.¹¹

- 5.2.4. Addenbrook’s Cognitive Assessment – Revised (ACE-R) is sensitive in the differential diagnosis of early stage dementia.¹² However, the design and psychometric properties is also suitable to provide information about cognitive functions and cognitive deficits in patients without dementia after a stroke.¹³ The ACE-R consists of five domains including attention/orientation, memory, verbal fluency, language and visuospatial ability.¹⁴ The total score in ACE-R is ‘100’ points, higher scores indicates better cognitive functioning. ACE- R scale was found as reliable and valid in Turkish population.¹⁵
- 5.2.5. Frenchay Activities Index (FAI) is a measure of instrumental activities of daily living (IADL) for use with patients recovering from stroke.¹⁶ The FAI assesses a broad range of activities associated with everyday life. The benefit of the FAI is that while activities of daily living scales tend to focus on issues related to self-care and mobility and it is an appropriate measure for functional outcome in stroke patients.¹⁷ The FAI comprises 15 activities, each of which is scored on a 4-point scale (0 to 3), to yield a total score ranging from 0 (inactive) to 45 (active). Scoring is based on the frequency with which the activities are carried out. It can be broken down into three subscales: domestic chores, leisure/work, and outdoor activities. Each subscale's score ranges from 0 to 15.¹⁸

6. Statistical Methodology

The statistical analysis will be carried out using the statistical package SPSS version 24.0. The variables will be reported by percentage (%) and mean \pm standard deviation ($x \pm sd$). Shapiro-Wilk test will be used to determine whether the data had a normal distribution. Pearson’s Chi-Squared Test and Fisher’s Exact Test will be used for comparison of the categorical data between the groups. Mann-Whitney U test will be used to analyze the intergroup differences, and Wilcoxon Signed-Rank Test will be used to analyze the intragroup differences. $P < 0.05$ will be accepted as the statistically significant level. The arithmetic means will be presented with a 95% confidence interval (95% CI) with lower and upper limit values. Both “p” values and 95% CI values will be considered while interpreting the differences between the groups. To analyze the intergroup changes, effect sizes will be calculated with “Cohen’s d”. The effect sizes will be interpreted as small effect ($d \geq 0.2$), medium effect ($d \geq 0.5$) and large effect ($d \geq 0.8$).[30]

The mean difference (MD) will also calculated to evaluate the change from the baseline to post-treatment as mean change \pm standard deviation.

7. References

1. van der Lee JH, Wagenaar RC, Lankhorst GJ, Vogelaar TW, Devillé WL, Bouter LM. Forced Use of the Upper Extremity in Chronic Stroke Patients. *Stroke*. 1999. doi:10.1161/01.str.30.11.2369

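### Time since stroke is neither restricted at entry, balanced at allocation nor used in the analysis, so mixed recovery stages can cost precision in the primary comparison and confound the within-group tests

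*Combined protocol and SAP*

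**What the plan says.** Eligibility (section 2) covers "The participants who are being diagnosed as first time ever stroke, who has hemiparesis, who are between the ages of 18-70". It adds a cognitive threshold, a global disability limit ("whose functional level is less than 4 according to the Modified Rankin Scale") and a tone limit ("upper extremity spasticity < 3 on Modified Ashworth Scale"). Exclusions include "limitation in passive normal joint movement in hemiplegic side" and "botulinum toxin administration or surgical operation in the last 6 months". That last item is the only time window among the criteria, and it does not concern the stroke.

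Allocation (section 2) is simple randomisation by odd and even numbers, with no stratification described.

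The primary outcome (section 5.1) is the WMFT at baseline and at week 8: "The change in scores from Baseline to 8 weeks will be calculated". The total score is capped at 75.

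The analysis (section 6) uses the Mann-Whitney U test between groups and the Wilcoxon signed-rank test within groups. No covariate or stratum is named.

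The sample size (section 3) is 15 per group, raised by 33% to 20. The mean and SD come from a cited trial and are not given.

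**The concern.** In the readable text a patient a few weeks after stroke and a patient several years after stroke are equally eligible. The first may gain arm function over 8 weeks with no training at all, while the second probably gains little. When both kinds enter, part of the spread in the 8-week change reflects stroke stage and not virtual versus real boxing.

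Two things are at stake:

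- **Primary between-group comparison.** The extra spread lowers precision. With 15 to 20 per arm and no stratification, the arms can also differ by chance in their share of recent strokes. The planned analysis does nothing to remove either effect.
- **Within-group tests.** Both groups box and there is no untreated group. A significant Wilcoxon result in either group cannot separate training from spontaneous recovery, and randomisation gives no protection here.

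**Working it through.** **1. The plan's own figure.** The step from 15 to 20 reproduces: 15 × 1.33 = 19.95, rounded up to 20. The 15 itself does not, because no effect size, SD or power is stated. Inverting it (two-sample t-test, two-sided α = 0.05, noncentral t), 15 per arm corresponds to a standardised difference of 1.06, 1.23 or 1.36 at 80%, 90% or 95% power. The steps below use d = 1.06, which gives 80% at 15 per arm and 90% at 20.

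**2. Variance from mixed stages.** Assume a share f of patients is early after stroke and gains an extra δ SD in either arm. The variance of the change is then multiplied by

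1 + f(1 − f)δ²

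and the effective difference becomes 1.06 / √(that factor). For f = 1/3 and δ = 1 the factor is 1 + (1/3)(2/3)(1) = 1.22. The information lost is 1 − 1/1.22 = 18%, or about 7 of 40 patients.

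| f | δ (SD) | Variance factor | Power, 15 per arm | Power, 20 per arm |
|---|---|---|---|---|
| none | – | 1.00 | 80% | 90% |
| 1/3 | 0.5 | 1.06 | 78% | 89% |
| 1/3 | 1.0 | 1.22 | 72% | 84% |
| 1/3 | 1.5 | 1.50 | 63% | 76% |
| 1/2 | 0.5 | 1.06 | 78% | 89% |
| 1/2 | 1.0 | 1.25 | 71% | 83% |
| 1/2 | 1.5 | 1.56 | 61% | 74% |

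The values of f and δ are assumptions; the documents supply neither. Fifteen per arm is the case where the whole dropout allowance is used up, and 20 is the case with no dropout.

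**3. What adjustment recovers.** Simulating f = 1/3, δ = 1 at 15 per arm gives about 72% power for an unadjusted t-test, 67–68% for the planned Mann-Whitney test, and about 78% for a linear model with group and stage. In this set-up the model removes the extra gain whatever its size, so the 78% does not depend on δ. The 2-point gap from 80% is the price of the extra term.

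**4. Chance imbalance.** Treat the number of early strokes in each arm as binomial. The probability that the arms differ by 20 percentage points or more is 33% at 15 per arm and 24% at 20 for f = 1/3, and 36% and 27% for f = 1/2. With δ = 1, a 20-point difference moves the estimate by 0.20 × 1 = 0.2 SD. The standard error is √(2/15) = 0.37 SD at 15 per arm and √(2/20) = 0.32 SD at 20.

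**The case against.** Four counter-arguments carry weight.

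- **No bias in expectation.** Randomisation equalises natural recovery on average. A 0.2 SD shift is smaller than the standard error and is ordinary sampling error that the test already allows for. This stands: the issue for the primary comparison is precision.
- **Possible double counting.** If the cited trial enrolled a similar mix, its SD already contains the recovery variance, and 15 per arm already pays for it. This also stands. Adjustment would still gain precision in that case.
- **The planned number is 20, not 15.** At 20 per arm, power stays above 80% in the table unless δ reaches 1.5.
- **Broad entry is legitimate** in a trial recruiting from the community. Agreed; the remedy need not narrow it.

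A reader might also infer more than the documents support:

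- **That the primary test does not fit the population.** Section 5.1 does say the modified WMFT was made "to assess the motor abilities of chronic patients who had suffered mild to moderate stroke". The sentence before it says the original was developed "to examine the patients with moderate to severe upper extremity motor deficits". The 17-item version then described is tied to neither, so no mismatch is shown.
- **That ceiling scores will cut power.** No criterion measures active arm function at the mild end, so scores near 75 are possible. But no baseline WMFT distribution is given, current hemiparesis is required, and section 1 says only 12% of patients with arm impairment regain full function. Any assumed share at ceiling lacks a source.
- **That severity is unrestricted.** The disability, spasticity and passive-movement criteria limit it indirectly, mainly at the severe end.

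The study diagram is not shown, so a criterion that appears only there cannot be ruled out.

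**Conclusion.** The point holds as a matter of precision and interpretation. Stroke stage is uncontrolled at entry, allocation and analysis in the readable text, and simple means are available to deal with it. The size of any loss is conditional: roughly 2 to 19 percentage points of power at 15 per arm and 1 to 16 at 20 per arm. This assumes that one third to one half of patients are early after stroke, with an extra gain of 0.5 to 1.5 SD, a true difference of 1.06 SD and a two-sided t-test. It would be smaller if the borrowed SD already includes such a mix. It would be wrong to say that the trial is shown to be underpowered or that its between-group estimate is biased.

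The within-group problem needs none of these numbers. Without an untreated group, the Wilcoxon tests cannot attribute change to training if recent strokes are enrolled.

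**What to change.** 1. Record months since stroke at baseline.
2. Fix one early/chronic cut-point in the SAP before any results by group are seen.
3. Include that stratum in the primary WMFT comparison, as a covariate in a linear model of the change or through a stratified rank test, and state which.
4. If enrolment has not begun, stratify the allocation list by it. Sections 5.2.1 and 5.2.2 are partly in the past tense, so this may be too late; items 1 to 3 would still be possible.
5. State in section 6 that the within-group Wilcoxon tests are descriptive and will not be read as evidence of a training effect.

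Naming the WMFT version in section 5.1 would also remove an ambiguity.

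The cost is one baseline field and one model term, with no extra visit. If stage turns out not to matter, the term costs about 2 points of power at 15 per arm. A cap on baseline WMFT at entry is an optional eligibility trade-off, since it narrows the population and slows recruitment. It is not part of this fix.

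### The odd/even allocation rule is not matched to the planned 20 + 20, and the readable text gives no number source, no concealment step and no rule for reaching equal arms

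*Combined protocol and SAP*

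**What the plan says.** SAP section 2 (Study design) screens patients for eligibility and then assigns them at random by "simple randomization (odd - even numbers: odd numbers will represent VBG and even number will represent RBG". Nothing in the readable text says whether the numbers come from a random-number source or from the order of entry. It also does not say who generates or holds them, or when the assignment becomes visible.

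Section 3 (Sample size calculation) reports that "Statistical power analysis calculations suggested 15 subjects for each group". It then raises this by 33% for dropout, with "finally 20 subjects planned to be included for each group". The same section also states "we will enroll 40 individuals in each treatment group", which contradicts 20 + 20. I read the intended total as 40, and the sentence should be corrected.

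No blocking, no rule for closing an arm and no masking of assessors is described. Section 2 refers to a CONSORT diagram for the study protocol. That figure is not shown in this copy, so every statement about missing detail here concerns the readable text only.

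**The concern.** The plan names an unrestricted method and a fixed arm size together. Unrestricted random draws leave the arm sizes to chance. An exact 20 + 20 needs a restriction, and the most obvious informal one, closing whichever arm fills first, makes the remaining assignments known. Odd/even can also mean the enrolment number, in which case the sequence is alternation.

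Foreknowledge matters here for four reasons:

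- Virtual and real boxing cannot be mistaken for each other, so staff who deliver sessions see past assignments.
- Several entry criteria in section 2 call for judgement: the Ashworth and Rankin limits and restricted passive joint movement.
- The primary outcome (section 5.1) is a rated functional score.
- Section 6 compares the arms with a Mann-Whitney test and plans no covariate adjustment for baseline, so an imbalance created at entry would pass into the comparison. Adjustment could in any case remove only the measured part.

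**Working it through.** **Inputs.** From section 3: 15 per group before dropout, 33% inflation, 20 per group, alpha 0.05. From section 2: odd/even assignment labelled simple randomization. Not given: power, effect size, SD and the source of the numbers.

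**The plan's own figure.** 15 × 1.33 = 19.95, rounded up to 20, which reproduces the stated 20 per arm. The 15 itself cannot be reproduced without the means, SD and power.

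**Reading 1: free random draws, 40 patients.** The size of one arm is Binomial(40, 0.5).

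- P(exactly 20:20) = C(40,20)/2^40 = 137,846,528,820 / 1,099,511,627,776 = 12.5%, so the arms are unequal 87.5% of the time.
- P(24:16 or worse) = 2 × P(X ≤ 16) = 26.8%.
- P(26:14 or worse) = 2 × P(X ≤ 14) = 8.1%.

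*Effect on power.* Assume a two-sided t test at 0.05, used as a stand-in for the Mann-Whitney test, all 40 patients analysed, and an effect size solved so that 15 + 15 gives the assumed power:

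| Assumed power at 15 + 15 | Implied d | 20:20 | 16:24 | 14:26 |
|---|---|---|---|---|
| 80% | 1.06 | 90.4% | 89.2% | 87.6% |
| 90% | 1.23 | 96.6% | 95.9% | 95.0% |
| 95% | 1.36 | 98.8% | 98.5% | 98.0% |

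In the first row the loss is 90.4 − 89.2 = 1.2 points at 16:24 and 90.4 − 87.6 = 2.8 points at 14:26. It is smaller in the other rows.

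**Reading 2: random draws, with an arm closed at 20.** The first arm fills at draw m with probability 2 × C(m−1, 19)/2^m, for m = 20 to 39. The remaining 40 − m assignments are then forced. Their mean is 40 × C(40,20)/2^40 = 40 × 0.1254 = 5.0, with median 4 and 90th percentile 9. The plan does not state this closing rule. It is one way the fixed 20 + 20 could be met.

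**Reading 3: running numbers.** After 40 patients the arms are exactly 20:20, and all 40 assignments are known in advance.

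**What steering could do (an illustration resting on assumptions).** Suppose there is no treatment effect, outcomes are normal, and k of 20 patients in one arm are 1 SD better in prognosis while k of 20 in the other are 1 SD worse. The mean shift is 2k/20 SD. Simulating 40,000 trials with the planned Mann-Whitney test at 0.05 gives false-positive rates of about 7% for k = 2, 11% for k = 3 and 17% for k = 4, against 5% for k = 0.

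**Guessability of the alternatives.** Assume past assignments are visible and the guesser always names the arm that is behind. Expected correct guesses out of 40:

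- Pure simple randomization: 20.0.
- Arm closed at 20: 20 + 5.01/2 = 22.5.
- One random permutation of 20 + 20: 20 + 2^39/C(40,20) − 0.5 = 20 + 3.99 − 0.5 = 23.5.
- Varying blocks of 2, 4 and 6: about 28 (simulation).

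**The case against.** The strongest reply is that section 2 speaks of random assignment and simple randomization, and that reading odd and even digits from a random-number table is an ordinary way to do this. Under true simple randomization past assignments say nothing about the next one, so seeing them does no harm. The 20 per arm is a recruitment target, and missing it by a few patients costs little. Section 2 also places eligibility before randomization, and the unseen diagram may carry the allocation details. All of this stands as far as it goes.

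It also rules out three stronger conclusions that a reader might draw:

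- *That the method cannot give 20 + 20 and also makes assignments foreseeable.* These faults belong to different readings. Free draws are unforeseeable but rarely balance; running numbers balance but are foreseeable. They coincide only if an arm is closed at 20, and then only for the last few patients. The documents do not say which reading applies, so foreseeability is a possibility left open, not something shown.
- *That an arm below 15 leaves the trial underpowered.* The calculation concerns 15 + 15. A 14:26 split has an effective size per arm of 2 × 14 × 26/40 = 18.2, and 87.6% power against the assumed 80%. With all 40 analysed, power drops below the 15 + 15 level only at 9:31 or worse, a 0.07% chance.
- *That patients have been steered.* Nothing in the documents says so, and the false-positive figures above are only an illustration.

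The reply does not settle where the numbers come from, how an assignment is concealed, or how the planned 20 + 20 is to be met. None of these can be answered from the readable text.

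**Conclusion.** The point holds as a gap in the specification of sequence generation and concealment, together with a mismatch between the method and the fixed arm sizes. Depending on what odd/even means, the plan has an 87.5% chance of missing 20 + 20, or about 5 assignments known in advance on average, or all 40 known in advance.

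The case rests on selection bias and on the mismatch with 20 + 20, not on power. It assumes a total of 40, equal chances per draw in the first two readings, and that the missing diagram does not supply the detail. The design is titled a randomized controlled study, and selection at entry cannot be fully repaired in the analysis, so the allocation procedure should be settled in the plan.

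**What to change.** - Replace the odd/even rule in section 2 with a computer-generated 1:1 list totalling 20 + 20. Use either one random permutation of 40 or larger, undisclosed, varying blocks that sum to 40, without blocks of 2.
- Have the list prepared by an existing team member who does not screen patients.
- Release each assignment by sequentially numbered, opaque, sealed envelope, only after eligibility, consent and baseline WMFT are recorded.
- For patients already allocated, report how their numbers were generated. If they were running numbers, do not describe the method as simple randomization. Apply the new list to the remaining patients.
- Correct the sentence in section 3 that gives 40 per group, so that it agrees with 20 + 20.

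The cost is revised wording, one list and a set of envelopes. There is one small downside: when past assignments are visible, a restricted list is somewhat more guessable than pure simple randomization (23.5 expected correct guesses against 20.0 for the single permutation). Small blocks widen that gap, which is why blocks of 2 should be avoided.

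### The plan allows for losing 5 of 20 patients per arm but does not provide for following or analysing them, so the primary comparison becomes an available-case analysis by default

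*Combined protocol and SAP*

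**What the plan says.** Section 3 gives the sample size in two steps. First, "Statistical power analysis calculations suggested 15 subjects for each group". Then, "considering the dropouts the number was increased by 33% and finally 20 subjects planned to be included for each group". Section 2 states the allocation: "Each participant will be randomly assigned to either treatment group with simple randomization".

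Section 5.1 fixes when the primary outcome is taken: "It will be measured at baseline (0 weeks) and at the completion of the treatment (8 weeks". There is no visit in between. It adds: "The change in scores from Baseline to 8 weeks will be calculated".

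Section 6 names the test: "Mann-Whitney U test will be used to analyze the intergroup differences". In the readable text neither section 6 nor any other section names an analysis population or an as-randomised principle. None provides for assessing patients who stop training, gives a rule for missing week-8 values, or plans a sensitivity analysis. Section 2 refers to a CONSORT diagram that is not shown in the text available, so an entry there on follow-up or analysed numbers cannot be excluded.

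**The concern.** Three parts of the plan point the same way. The inflation in section 3 restores 15 evaluable patients after dropout, so it budgets for dropouts who contribute no outcome. The endpoint in 5.1 needs a value taken at the end of treatment. The test in section 6 uses only patients who have that value. Nothing readable pulls in the other direction.

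Randomisation makes the two groups comparable as randomised. It does not make the subgroups with a week-8 value comparable. If patients doing poorly leave one arm more readily than the other, the arm they leave looks better than it is. With no intermediate visit, the data would hold only baseline information on a patient who was lost. Up to 10 of 40 patients could be affected within the plan's own allowance, and how to treat them would be decided after the data are in.

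**Working it through.** **Step 1: the plan's own figure.** Inputs from section 3: 15 per arm, raised by 33%.

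- 15 × 1.33 = 19.95, rounded up to 20. The stated figure is reproduced.
- Implied loss: (20 − 15)/20 = 5/20 = 25% per arm, or 10 of 40 overall.
- If 33% were the loss rate itself, the plan would need 15/(1 − 0.33) = 22.4, so 23 per arm. That does not match 20, so 33% is the inflation and 25% is the loss allowed for.

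The base figure of 15 cannot be reproduced. Section 3 says only "The mean and standard deviation values are taken as a reference from the study" cited, without the values, and gives neither power nor sidedness. For scale, 15 per arm (t-test, two-sided α = 0.05) detects d = 1.06, 1.23 or 1.36 at 80%, 90% or 95% power.

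**Step 2: how far missing values can shift one arm.** With a fraction *m* missing, mean of those observed − mean of all randomised = *m* × (mean of observed − mean of missing). With *m* = 0.25:

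| Assumed gap, observed vs missing (SD) | Shift in that arm (SD) |
|---|---|
| 0.25 | 0.06 |
| 0.5 | 0.13 |
| 0.8 | 0.20 |
| 1.0 | 0.25 |

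If only one arm is affected, this shift is the bias in the group difference. If both arms shift equally, it cancels.

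**Step 3: effect on the Mann-Whitney test.** Assumptions: no true difference, normal change scores with SD 1, exactly 20 per arm, 5 lost from each arm, two-sided test at 0.05 on 15 against 15. Loss depends on a score that correlates ρ with the patient's change. The values of ρ are assumed; the documents give none.

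Hand check of the one-arm bias: removing the lowest 25% of a normal distribution raises the mean by 0.318/0.75 = 0.42 SD, so the bias is about ρ × 0.42. That gives 0.21, 0.29 and 0.42 SD for ρ = 0.5, 0.7 and 1.0. Simulation (20,000 trials per setting) gives slightly less, because the arms are small:

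| Loss mechanism | Bias (SD) | Type I error |
|---|---|---|
| Random in both arms | 0 | 4.5% |
| ρ = 0.5 in one arm, random in the other | 0.20 | 8% |
| ρ = 0.7 in one arm, random in the other | 0.29 | 12% |
| ρ = 1.0 in one arm (the five worst leave), random in the other | 0.41 | 22% |
| ρ = 0.5 in one arm, 0.3 in the other | 0.08 | 6% |
| ρ = 0.5 in both arms | 0 | 5% |
| ρ = 0.7 in both arms | 0 | 6% |
| ρ = 1.0 in both arms | 0 | 10% |

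Shorter runs of 4,000 to 8,000 trials gave 7% to 9% for the mildest one-arm case and 20% to 22% for the extreme one.

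**Step 4: what the remedies can do.** Imputing from one baseline score by arm (single regression imputation, one-arm loss at ρ = 0.5) moves the bias from 0.20 to 0.20 SD if baseline is unrelated to change, from 0.21 to 0.19 if they correlate 0.3, and from 0.20 to 0.16 if they correlate 0.5. Retrieval does more. By the formula in step 2, if the missing fall from 5 to an assumed 2 of 20, then *m* = 0.10, and a gap of 0.8 SD gives 0.10 × 0.8 = 0.08 SD instead of 0.20.

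**The case against.** The strongest reply is that this reads a design into silence. Several inferences that a reader might draw are indeed not supported.

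- *That the plan prescribes a completers-only analysis.* It never says so. Inflating enrolment protects power and is compatible with an as-randomised analysis. The week-8 wording can be read as a visit label, and nothing bars assessing a patient who stopped training. A patient who stopped but returned at week 8 would be included, so available-case is the accurate term.
- *That the plan predicts a loss of 5 in 20.* The figure is a planning allowance, neither a forecast nor a cap.
- *That dropout will differ by arm because the two trainings differ in setting or physical demand.* The documents name virtual and real boxing but describe neither the setting nor the intensity of either.
- *That the result will be biased.* Bias in the group difference needs loss that differs between arms in amount or in its relation to response. With the same mechanism in both arms it is near 0.

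All four limits stand. They change the wording and the certainty, but they do not remove the point. A Mann-Whitney test, whether on the change or on the week-8 score, still drops every patient without a week-8 value, and the readable text makes no provision for obtaining that value from patients who stop.

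**Conclusion.** The point holds as an exposure to bias, not as a demonstrated bias. Followed as written, the primary comparison is by default an available-case analysis, with an allowance of 25% missing per arm.

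At that level of loss, a response-related mechanism in one arm only gives a bias of about 0.2 to 0.4 SD and a type I error of about 8% to 22%. A shared mechanism gives bias near 0 and about 5% to 10%. On section 6's own scale, where d of 0.2 or more counts as a small effect, the one-arm cases could create or hide a small effect. They stay below 1.06, the smallest of the detectable effects worked out for 15 per arm.

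These sizes rest on assumed correlations, normal change scores and the full allowance being used. The documents do not say which pattern applies, so neither the direction nor the size of any real bias can be computed from them. The statement that the plan makes no provision is limited to the readable text, because the CONSORT diagram could not be checked.

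**What to change.** - **Section 5.1:** state that the week-8 WMFT is sought from every randomised patient at 8 weeks from baseline, whether or not training was completed. This matters most, because it reduces the missing data instead of modelling them.
- **Section 6, analysis set:** state that the primary analysis compares patients in the group to which they were assigned, using all week-8 values obtained.
- **Section 6, sensitivity:** add a best-case/worst-case analysis for values still missing: favourable values in one arm and unfavourable in the other, then reversed. With many missing values the range will be wide; it is a bound, not an estimate.
- **Imputation, if wanted:** keep multiple imputation as a sensitivity analysis with a small model (baseline WMFT-FAS and arm). With about 15 observed patients per arm, a model with several baseline scores fitted within each arm would be unstable. Where loss depends on the unseen change, imputation from baseline removes little of the bias.
- **Reporting:** give the number lost and the reasons by arm, so that readers can judge whether the pattern was similar.

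The cost is a few sentences in the SAP, some effort to bring back patients who stopped training for an assessment already planned, and a little extra analysis. Bias from values that remain missing is bounded by the sensitivity analysis, not removed.
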